#### **9.15 Single-Nucleotide Polymorphism Analysis**

A SNP assay will be performed at Screening on a blood, buccal, or saliva sample to identify polymorphisms in the ZFN-targeted region of the albumin locus. For post-transplant subjects, the assay will be performed on saliva samples only. For pediatric subjects (cohorts 4 through 7), saliva samples are strongly preferred. Subjects with polymorphisms in the ZFN-targeted region of the albumin locus are not eligible to participate in this study. For details, refer to the Laboratory Manual.

#### **9.16 Viral Load**

Testing for HIV, HBV, and HCV will be conducted at Screening. Subjects with a diagnosis of HIV or evidence of active HBV or HCV infection are not eligible to participate in this study. For details, refer to the Laboratory Manual.

#### **9.17 Neutralizing Antibodies to AAV2/6**

The level of neutralizing antibodies to AAV2/6 will be measured at Screening to assess the subject's pre-existing immune response to AAV2/6. Subjects with elevated pre-existing neutralizing antibodies to AAV2/6 are not eligible to participate in this study. For details, refer to the Laboratory Manual.

#### **9.18 Chimerism Assay**

The chimerism assay is a routine post-transplant monitoring tool to evaluate the ratio of donor-to-recipient white blood cells in peripheral blood. The assay will be performed on blood samples in post-HSCT subjects to evaluate the safety of SB-318 with respect to any potential impact on the donor graft. Baseline chimerism prior to SB-318 will be established by analyzing blood samples in conjunction with HSCT-donor specific and subject-specific genetic markers as provided by the original transplant center. In instances where this data is not available from the transplant center, baseline chimerism can be determined from buccal swabs and peripheral blood samples analyzed in parallel. For details, refer to the Laboratory Manual.

#### **9.19 GAG Testing in Urine and Blood**

GAGs are metabolites that accumulate in MPS I due to lack of active IDUA enzyme. GAG accumulation is responsible for diffuse organ toxicity and damage in MPS I. To monitor the effect of SB-318 administration, GAG levels (including total GAG, DS GAG, and HS GAG) will be measured in urine and tissues (including blood, liver tissue, and CSF) throughout this study. Samples for GAG testing in blood and urine must be obtained 7 days after ERT administration (+/- 1 day) and prior to the next ERT infusion. GAG and IDUA levels in blood will both be measured concurrently from the same blood sample. For details, refer to the Laboratory Manual.

#### **9.20 Circulating AFP Level**

Clinical laboratory measurement of AFP will be performed to monitor for potential development of malignancy. Subjects with elevated abnormal circulating AFP at Screening are not eligible to participate in this study. For details, refer to the Laboratory Manual.

## **9.21 Vector Genome PCR**

Plasma, saliva, stool, and semen (males only) samples will be analyzed by PCR to determine clearance of SB-318 vector genomes. Each type of sample (plasma, saliva, urine, stool, semen) should be collected until 3 consecutive specimens of that sample type are reported as negative or undetectable for vector genome. Collection of semen samples may be waived for pediatric subjects (cohorts 4 through 7) at the discretion of the Principal Investigator. For details, refer to the Laboratory Manual.

## **9.22 Pulmonary Function Tests**

MPS I is often associated with significant pulmonary complications. Pulmonary function tests (PFTs) are a common method for evaluating respiratory function, and will be conducted in this study as permitted by the subject's capacity. For details, refer to the Study Reference Manual.

## **9.23 6-Minute Walk Test**

A 6-minute walk test (6MWT) will be performed, as permitted by subject's capacity, to measure endurance following the American Thoracic Society Guidelines. For details, refer to the Study Reference Manual.

## **9.24 Visual Acuity Test and Corneal Clouding Exam**

Corneal clouding and vision loss are common complications of MPS I. A standard visual acuity exam and inspection of both eyes will be performed to determine the absence or presence of corneal clouding. For details, refer to the Study Reference Manual and the Physical Exam Guidelines.

## **9.25 Neurocognitive Abilities Tests**

WASI-II, WPPSI-IV, and BSID-III are widely-used neurocognitive tests that have been validated and are easily administered. Given the broad age-range of study participants and variability of CNS involvement due to MPS I, the appropriate test will be determined for each subject at Screening following a neurocognitive abilities assessment. VABS-II will be used to perform the neurocognitive abilities assessment. Based on this initial evaluation, either the WASI-II, the WPPSI-IV, or the BSID-III will be administered to each subject beginning at the Baseline visit. The same test should be used throughout the study duration when possible to allow for longitudinal evaluation.

The VABS-II test is given to all subjects and provides a measure of adaptive behaviors, including ability to cope with environmental changes, to learn new skills, and to demonstrate independence.

The tests will be administered by a trained psychologist or psychometrist to determine neurocognitive function over time after SB-318 administration, as permitted by the subject's capacity. For details, refer to the Study Reference Manual.

## **9.26 MRI of Liver**

MRI of the liver is commonly used to evaluate liver pathology in patients with MPS I, and will be performed in this study to evaluate liver and spleen volumes, as well as to screen and monitor for the potential development of liver masses. For details, refer to the Study Reference Manual and the Imaging Guidelines.

### **9.27 MRI of Brain and Cervical Spine**

MRI of the brain and cervical spine is commonly used to evaluate neurological and skeletal complications in patients with MPS I, and will be performed in this study to evaluate for changes in clinical soft tissue and/or bone appearance. The baseline MRI of brain and cervical spine may be obtained at Screening (together with MRI for liver) instead of at Baseline at the Principal Investigator's discretion. For details, refer to the Study Reference Manual and the Imaging Guidelines.

### **9.28 Adrenocorticotropic Hormone Stimulation (Cosyntropin) Test**

An ACTH stimulation test will be performed prior to beginning and discontinuing a prednisone or equivalent corticosteroid regimen to evaluate adrenocortical function. During the test, vital signs should be monitored and recorded every hour. For details, refer to the Study Reference Manual.

### **9.29 IDUA Testing in Blood**

IDUA activity in blood will be measured to determine whether IDUA is being produced and is active. IDUA activity measurements may be conducted on plasma, serum, whole blood, dried blood spot, leukocytes, or other blood component. Samples must be obtained 7 days after ERT administration (+/- 1 day) and prior to the next ERT infusion. IDUA and GAG testing in blood will both be measured concurrently from the same blood sample. For details, refer to the Laboratory Manual.

### **9.30 Liver Biopsy**

The proposed mechanism of action of SB-318 is to introduce the hIDUA transgene into a precise location in the albumin locus. To determine the efficiency of SB-318, liver tissue will be obtained by liver biopsy, unless contraindicated by the Principal Investigator or physician, and analyzed by histopathologic examination, testing for GAG levels, and high-throughput sequencing of the albumin locus. Further, subjects with an elevated AFP or MRI mass suspicious for HCC or greater than 2 cm will undergo liver biopsy. Histopathologic examination and genomic analysis will be performed to determine the origin and nature of the tumor. For details, see [Appendix 4](#) and refer to the Study Reference Manual.

### **9.31 Lumbar Puncture**

MPS I often causes neurocognitive decline due to a buildup of GAGs in the brain. To determine if GAG levels in the CSF are changed after SB-318 administration, lumbar punctures will be performed on all subjects, unless contraindicated by Principal Investigator or physician. CSF samples may also be tested for cell count, total protein, glucose, and other MPS-related biomarkers. For details, refer to the Study Reference Manual.

### **9.32 Immunogenicity Assays**

Exploratory research assays, including total antibodies to AAV2/6, ZFN, and IDUA immunogenicity will be performed. At the discretion of the Principal Investigator, this assessment may be waived for pediatric subjects (cohorts 4 through 7) to reduce required blood volumes. For details, refer to the Laboratory Manual.

### **9.33 Laboratory Assessments in Pediatric Subjects**

Although safety monitoring of subjects with clinical laboratory testing is necessary in this study, the potential impact of taking multiple blood samples in children must be assessed at all times.

Therefore, all blood draws in pediatric cohorts should be minimized when possible to ensure the safety and welfare of the subjects, particularly in the case of younger children. In accordance with accepted guidance, no more than 1% of total blood volume (0.8 mL/kg) should be drawn in pediatric subjects in any 24-hour period unless medically-indicated based on the judgement of the Principal Investigator ([Veal et al, 2014](#)). In addition, it is encouraged to utilize procedures to minimize any pain and distress associated with blood sampling when possible, such as use of intravenous catheters, collection from central catheters if in place, and use of local anesthesia for needle sticks. For details, refer to the Laboratory Manual.

#### **9.34 ERT Administration Log**

Frequency of ERT administration will be studied before and after administration of SB-318. Therefore, each dose of ERT given to the subject from the time of Screening will be recorded on the ERT Administration Log by study staff and will include date and time of start and stop of ERT infusion. At each indicated visit, documentation of all ERT administration since the last visit must be obtained and confirmed. An assumed standing schedule (e.g., weekly) should not be used.

#### **9.35 ERT Clinical Assessment**

A clinical assessment of the need for ERT must be conducted at the ERT Withdrawal Follow-Up visit. The Principal Investigator should determine if chronic weekly ERT infusions will be resumed or if the subject may continue without ERT, and indicate the decision on the appropriate eCRF. The assessment will be made based on the clinical judgement of the Principal Investigator and in consultation with the Medical Monitor, taking into account all information available (which may include but is not limited to AEs, clinical laboratory testing, IDUA levels, GAG levels, 6MWT, PFTs, and other available data). The ERT Clinical Assessment may be completed again at any time post-ERT withdrawal if there is a clinically significant change in the status of the subject's ERT administration.

## **10 SAFETY MONITORING AND ADVERSE EVENTS**

### **10.1 Definitions**

#### **10.1.1 Adverse Event**

An AE is any untoward medical occurrence in a patient or a clinical trial subject administered a medicinal product. An AE does not necessarily have a causal relationship with the administered treatment. The term can include any of the following events that develop or increase in severity during the course of this study:

- Any sign, symptom, or physical examination finding that worsens in nature, severity, or frequency compared to Baseline, whether thought to be related or unrelated to the condition under study.
- Any clinically significant laboratory abnormality or laboratory abnormality that requires medication or hospitalization.
- All reactions associated with the use of the study treatment, including those occurring as a result of an overdose, abuse, withdrawal phenomena, sensitivity, or toxicity to the study treatment.
- Concurrent illness.
- Injury or accident.

A pre-existing condition is one that is present prior to or at the start of the study, and is to be reported as part of the subject's medical history. It should be reported as an AE only if the frequency, intensity, or the character of the condition worsens during study participation.

#### **10.1.2 Adverse Reaction**

An AR is any untoward and unintended response to a medicinal product related to any dose administered. The phrase "response to a medicinal product" means that a causal relationship between the medicinal product and the AR is at least a reasonable possibility (i.e., there are facts/evidence or arguments to suggest a causal relationship).

The definition of an AR also covers medication errors and uses outside what is foreseen in the protocol, including misuse and abuse of the product.

#### **10.1.3 Unexpected Adverse Event or Adverse Reaction**

An Unexpected AE or Unexpected AR is an AE or AR, the nature or severity of which is not consistent with the reference safety information (RSI) for the product (e.g., Investigator's Brochure).

#### **10.1.4 Serious Adverse Event or Serious Adverse Reaction**

An AE or AR is considered "serious" if, in the view of either the Principal Investigator or the Sponsor, it results in any of the following outcomes:

- Death.
- Life-threatening AE (i.e., AE in which the subject was at risk of death at the time of the event; it does not refer to an event which hypothetically might have caused death if it were more severe).

- Inpatient hospitalization or prolongation of existing hospitalization.
- Persistent or significant incapacity or substantial disruption of ability to conduct normal life functions.
- Congenital anomaly/birth defect in the offspring of an exposed subject.
- Important medical event that may jeopardize the subject or may require an intervention to prevent one of the above characteristics/consequences (i.e., event may not result in death, be life-threatening, or require hospitalization, but based on appropriate medical judgment, it may jeopardize the subject and may require medical or surgical intervention to prevent one of the outcomes listed above; examples include allergic bronchospasm requiring intensive treatment in an emergency room or at home, blood dyscrasias or convulsions that do not result in inpatient hospitalization, and development of drug dependency or drug abuse).

With regard to results obtained from tests in laboratory animals or *in vitro* testing, whether or not conducted by Sangamo, a SAE includes any event suggesting significant risk to human subjects.

#### **10.1.5 Suspected Unexpected Serious Adverse Reaction**

A suspected unexpected serious adverse reaction (SUSAR) is any SAE that is assessed as both unexpected and, in the view of either the Principal Investigator or the Sponsor, as an AR.

#### **10.2 Adverse Event Reporting Period**

AEs will be monitored continuously during the study from the time that the subject has provided written informed consent through the subject's last day of study participation. Subjects will be queried and events will be assessed at each clinic visit. A treatment-emergent AE (TEAE) is any AE with an onset from any time from administration of the study treatment through the last study visit, whether or not it is considered causally related to the study treatment.

#### **10.3 Recording of an Adverse Event**

The Principal Investigator is responsible for evaluating all AEs, obtaining supporting documents, and determining that documentation of the event is adequate. He/she is responsible for determining the severity of the AE and its relationship to the investigational drug. The Principal Investigator may delegate these duties to sub-investigators but must assure that these sub-investigators are qualified to perform these duties under the supervision of the Principal Investigator.

All AEs will be recorded in the subject's CRF. The detailed description of the event will include appropriately graded severity of the AE and its relationship to the investigational product. Severity will be categorized by toxicity grade according to the Common Terminology Criteria for Adverse Events (CTCAE) Version 4.03.

AEs not listed in the Common Terminology Criteria for Adverse Events version 4.03 will be evaluated by using the following criteria:

- Grade 1, Mild: Symptoms cause no or minimal interference with usual social and functional activities.
- Grade 2, Moderate: Symptoms cause greater than minimal interference with usual social and functional activities.

- Grade 3, Severe: Symptoms cause inability to perform usual social and functional activities.
- Grade 4, Potentially Life-threatening: Symptoms cause inability to perform basic self-care functions OR medical or operative intervention indicated to prevent permanent impairment, persistent disability, or death.
- Grade 5: Outcome of AE is death.

The relationship of the AE to the investigational drug will be determined by the Principal Investigator. Any AE that does not meet the definition of a suspected AR will be categorized as Not Related.

Any Grade 3 and 4 clinical laboratory results that represents an increase in severity from Baseline will be reported as an AE if it is not associated with a diagnosis already reported on the CRF. A Grade 1 or 2 clinical laboratory abnormality should be reported as an AE only if it is considered clinically significant by the Principal Investigator.

In the event of death, the cause of death should be recorded as the AE and reported as a SAE. "Death" is not the AE; "death" is an outcome. The term "death" should be reported as an SAE only if the cause of death is not known and cannot be determined. If an autopsy is performed, a copy of the autopsy report should be obtained if possible. The Principal Investigator should make every effort to obtain and send death certificates and autopsy reports to Sangamo.

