During the first 20 weeks after SB-318 infusion, liver function tests (aspartate aminotransferase [AST], alanine aminotransferase [ALT], total and direct bilirubin, alkaline phosphatase, LDH, albumin, and total protein levels) will be conducted for evaluation of AAV-mediated immunogenicity twice a week. The tests may be conducted remotely. Blood samples for these tests will be drawn 2 to 4 days apart when possible, except for the first week when they will be drawn on the Day 1 and Day 7 visits. Liver function tests will subsequently be conducted at all study visits.

Previous studies with IV AAV8 FIX gene therapy have shown that liver transaminitis due to AAV immunogenicity occurs between 2 and 9 weeks after infusion, and that rapid institution of prednisone can control this immunogenicity ([Nathwani et al. 2014](#)). If in spite of the pretreatment with prednisone or equivalent corticosteroid there is evidence of transaminitis, the dose of prednisone or equivalent corticosteroid will be increased on a case-by-case basis, and liver function will be assessed twice a week until normalization of liver enzymes, and then per protocol thereafter.

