### 11.2 Dose Escalation Rules

Within each cohort, treatment will be staggered so that each subsequent subject will not be infused until the preceding subject has been observed for at least 4 weeks following administration of SB-318.

Dose escalation to the next cohort will not occur until at least 4 weeks after the last subject in the preceding cohort has been dosed, the safety data from the prior cohort has been reviewed by the SMC, and the SMC has agreed to dose escalate.

Dosing and dose escalation will be paused if a Grade 3 or higher AE occurs, or if two Grade 2 AEs occur within the same organ class and persist for more than 2 weeks with therapy, provided these AEs are not related to the primary MPS I disease or treatment of the MPS I disease. In such an event, the SMC will be convened to assess for potential dose-limiting toxicity (DLT), and to provide recommendations on whether to expand the cohort at the same dose level, to dose de-escalate, or to continue the study as planned (refer to the [Stopping Rules](#)).

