## APPENDIX 3: IMMUNOSUPPRESSION REGIMEN

Weight of Subject (kg)	Oral Prednisone (mg/day)					
	Day -2 to Day 0	Week 1	Week 2	Week 3-16	Week 17-19	Week 20
≥ 60	60	60	30	15	5	STOP
55	60	60	30	15	5	STOP
50	50	50	25	15	5	STOP
45	45	45	25	15	5	STOP
40	40	40	20	10	5	STOP
35	35	35	20	10	5	STOP
30	30	30	15	10	5	STOP
<30	1 mg/kg	1 mg/kg	0.5 mg/kg	0.25 mg/kg	0.25 mg/kg every other day	STOP

Prednisone or equivalent corticosteroid regimen is commenced 2 days prior to Day 0 of SB-318 infusion and given once daily unless otherwise stated. Subject's liver function will be monitored twice a week while on prednisone or equivalent corticosteroid. Blood for liver panel shall be drawn 2 to 4 days apart when possible, except for the first week when it will be drawn on the Day 1 and Day 7 visits. Tapering of prednisone or equivalent corticosteroid will only proceed if ALT/AST activity levels are stable or declining (based on the 2 assessments of the preceding week).

If subjects develop increased ALT > 2 fold Baseline while on prednisone or equivalent corticosteroid or after stopping prednisone or equivalent corticosteroid, the prednisone or equivalent corticosteroid regimen may be adjusted or restarted at the Principal Investigator's discretion after consultation with the Medical Monitor.

Twice a week liver panel testing should continue until the prednisone or equivalent corticosteroid course has been terminated.

An ACTH stimulation (cosyntropin) test will be performed prior to the first prednisone or equivalent corticosteroid dose and again during Week 20 or at the end of the scheduled taper to ensure that the adrenal cortical function has not been suppressed. Should prednisone or equivalent corticosteroid treatment be repeated due to increased transaminase activity, the ACTH stimulation test will be repeated at the end of taper at the Principal Investigator's discretion.

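### Sections 10.1.1 and 10.3 disagree on whether a Grade 1-2 laboratory abnormality that needs medication is an AE, so a steroid-treated ALT/AST rise can go uncounted

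*Protocol*

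**What the plan says.** **Definition.** Protocol Section 10.1.1 introduces its list of AEs in permissive terms: "The term can include any of the following events that develop or increase in severity during the course of this study". The laboratory item reads "Any clinically significant laboratory abnormality or laboratory abnormality that requires medication or hospitalization". That gives two routes, joined by *or*, with no grade limit.

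**Recording.** Section 10.3 says that all AEs go into the CRF and then treats laboratory results by grade. For the higher grades, "Any Grade 3 and 4 clinical laboratory results that represents an increase in severity from Baseline will be reported as an AE", unless the result belongs to a diagnosis already on the CRF. For the lower grades, "A Grade 1 or 2 clinical laboratory abnormality should be reported as an AE only if it is considered clinically significant", and that judgement is the investigator's.

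**Steroid response.** Section 3.5 says that, for transaminitis despite prophylaxis, "the dose of prednisone or equivalent corticosteroid will be increased on a case-by-case basis". Appendix 3 covers the same ground with a relative threshold: "If subjects develop increased ALT > 2 fold Baseline while on prednisone or equivalent corticosteroid", or after it has been stopped, the investigator may adjust or restart the regimen after consulting the Medical Monitor. Neither place says whether the rise is then recorded as an AE.

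**Where AEs are used.** Section 13.4 makes TEAE incidence the primary endpoint. Section 11.2 pauses dosing for any Grade 3 or higher AE, or "if two Grade 2 AEs occur within the same organ class and persist for more than 2 weeks with therapy". Sections 11.5 and 12.3 convene the SMC on the same two conditions, among others. Events related to MPS I or its treatment are excepted from both conditions.

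**The concern.** Section 10.3 keeps only one of the two routes in 10.1.1 for Grade 1-2 results. The route it drops, a need for medication, is the one that fits the trial's main expected toxicity: transaminitis is the first key risk in Section 12.2, and the planned response to it is more steroid. No passage says that a steroid change makes a rise clinically significant.

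Two sites (12 to 15 are planned) could therefore record the same treated rise differently, and both could point to the protocol. Any loss goes one way, toward fewer recorded events, and it affects both the primary endpoint and a safety trigger that counts recorded AEs rather than laboratory values.

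**Working it through.** The plan states no figure on this point, so there is none to reproduce. The main check is to compare the two rules.

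**1. The rules side by side**

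| Laboratory abnormality | 10.1.1 | 10.3 |
|---|---|---|
| Grade 1-2, judged clinically significant | AE | Reported |
| Grade 1-2, not judged significant, needs medication or hospital care | AE | Not reported |
| Grade 1-2, neither | Not covered by the laboratory item | Not reported |
| Grade 3-4, worse than Baseline | AE by either route | Reported without a significance call, unless part of a diagnosis already on the CRF |

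Only the second row conflicts.

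**2. Does the steroid threshold fall in that row?**

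Inputs: the threshold is 2 x Baseline ALT (Appendix 3); entry ALT is at most 2.0 x ULN (exclusion criterion 8e, Section 4.2). I assume that Baseline stays within the entry limit. The documents cite CTCAE 4.03 without its cut-offs, so I assume Grade 1 above 1 x ULN, Grade 2 above 3 x ULN (2.5 also tried) and Grade 3 above 5 x ULN.

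- Baseline 0.5: 2 x 0.5 = 1.0 x ULN, no grade.
- Baseline 1.0: 2 x 1.0 = 2.0 x ULN, Grade 1.
- Baseline 1.5: 2 x 1.5 = 3.0 x ULN, Grade 1 (Grade 2 with the 2.5 cut-off).
- Baseline 2.0: 2 x 2.0 = 4.0 x ULN, Grade 2.

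The threshold is never above 4.0 x ULN, so it sits below Grade 3 for any Grade 3 cut-off higher than that. With the cut-off at 5, a rise stays at Grade 2 or lower up to 5/0.5 = 10-fold, 5/1.0 = 5-fold or 5/2.0 = 2.5-fold over Baseline.

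**3. Effect on incidence**

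Planned enrolment is 1 + 6 x 2 = 13. Two more subjects in each of the 7 cohorts gives 13 + 14 = 27, which agrees with the stated maximum. One unrecorded event changes incidence by 100/n points: 100 (n = 1), 50 (n = 2), 7.7 (n = 13), 3.7 (n = 27). This holds for the preferred term if the subject has no other event under that term. It holds for overall TEAE incidence only if the subject has no other TEAE.

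**4. Effect on the Grade 2 trigger**

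Suppose that two rises truly qualify and that each is independently judged clinically significant with probability q (assumed). Both are recorded with probability q x q: 1.00 at q = 1, 0.64 at q = 0.8, 0.25 at q = 0.5. This is illustrative only, because the documents give no basis for q. A Grade 1 rise never counts here, whether recorded or not.

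**5. Do other outputs restore the event?**

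- SAP 8.1.2 lists laboratory values with abnormal ones flagged. Its shift tables use low, normal and high, so a Grade 2 rise appears only as high.
- SAP 8.1.7 counts a subject once per medication preferred term. Every subject receives prophylactic corticosteroid, so an increase or restart of the same drug shows only in the listing.
- SMC cohort review includes laboratory results (Section 11.5), but can take place 4 weeks after the last subject is dosed. Section 3.5 cites transaminitis at 2 to 9 weeks in earlier AAV8 studies, so a later rise can come after that review.

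The values survive, but none of these outputs puts the event into TEAE incidence or the trigger count.

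**The case against.** The strongest reply is that the failure case is narrow. The investigator would have to consult the Medical Monitor, change the steroid because of an ALT rise, and still call that rise not clinically significant. Needing treatment is an obvious reason to call a value significant. Because 10.3 also requires every AE to be recorded, a site could treat 10.1.1 as decisive and use the Grade 1-2 sentence only to screen out incidental values. Most of this stands. It makes omission less likely, but it does not remove the words that restrict Grade 1-2 reporting to one route, and sites remain free to differ.

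Some stronger readings are tempting, and the documents do not support them:

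- *That 10.1.1 obliges a site to record every treated rise.* Its list is introduced as what the term can include, and Appendix 3 says that the regimen may be adjusted. Crossing twice Baseline does not by itself mean that medication is required.
- *That any doubling of ALT falls in the gap.* A rise from 0.4 to 0.8 x ULN stays within the normal range and is not a graded abnormality, so neither rule clearly governs it.
- *That the pause rule is disabled, or the SMC left unsighted.* Grade 3 or higher rises are still reported. The Grade 2 limb needs two events in one organ class lasting more than 2 weeks with therapy. The SMC sees laboratory results at cohort review and may be convened at any time for excessive or unexpected toxicity, and SAP Section 10 adds rolling reviews about every 4-6 months.

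The incidence shifts of 100 and 50 points also follow from cohorts of 1 and 2, and would apply to any single missed event.

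**Conclusion.** The two sections conflict, and the conflict should be removed. It is confined to Grade 1-2 laboratory abnormalities that need medication or hospital care but are not judged clinically significant. For ALT/AST rises treated with steroid, a literal reading of 10.3 allows omission from TEAE incidence and, for Grade 2 rises only, from the two-event trigger.

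The exposure is one event at a time, with the shifts shown above. Under-reporting is a possibility that the text permits; nothing in the documents shows that it has happened or will. The finding of conflict rests on the wording alone. Placing the steroid threshold below Grade 3 also assumes a Grade 3 cut-off above 4.0 x ULN and a Baseline within the entry limit.

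**What to change.** Reconcile Section 10.3 with 10.1.1 in the latter's own terms. For example, keep "A Grade 1 or 2 clinical laboratory abnormality should be reported as an AE only if it is considered clinically significant by the Principal Investigator" and continue the sentence with: *or requires medication or hospitalization*.

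For subjects already dosed, compare steroid changes made for ALT/AST rises with the AE page and query any rise that has no matching entry.

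Leave the steroid regimen and Sections 11.2, 11.5 and 12.3 alone: a recorded Grade 2 AE already counts there. The added words should also go no further than 10.1.1. Making every extended steroid course an AE would do so, because Appendix 3 already holds the taper unless ALT/AST is stable or declining, and minor fluctuations would then be recorded.

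The cost is one sentence in an amendment and about one data query per dosed subject. The downside is a few more low-grade AEs, so reported TEAE incidence may look slightly less favourable.
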